## 2.2 Rationale

The overarching rationale for the proposal is that motor neuron hyperexcitability contributes to neurodegeneration in ALS and that reduction of neuronal hyperactivity may slow the disease course. The clinical neurophysiological techniques used to demonstrate hyperexcitability may be useful as biomarkers to indicate reduction in excitability with treatment. Studies involving clinical neurophysiology, mouse motor neuron models and human iPSC-derived motor neurons from ALS patients all suggest that motor neuron hyperexcitability may contribute to motor neuron death in ALS. In particular, *in vitro* treatment of ALS patient-derived motor neurons with ezogabine can reverse the hyperexcitability and improve motor neuron survival. On account of these data, the primary goal of this study is to determine whether ezogabine treatment safely reduces neurophysiological indices of motor neuron hyperexcitability in ALS subjects.

The upper dose limit for this study was chosen based on tolerability in previous epilepsy studies (Porter et al, 2007; Brodie et al, 2010; French et al, 2011). Oral doses of 600 mg/day (all doses divided TID), 900 mg/day, and 1200 mg/day were used in two of the three studies. At 1200 mg/day, subject drop out due to AEs was nearly 30% (vs. 20% in the 900 mg/day dose) in Porter et al. (2007). On the opposite end, there was no statistically significant benefit in the 600 mg/day dose compared to placebo, while a clear reduction in seizure frequency was observed with 900 and 1200 mg/day treatments. There is no indication, given the stable linear PK properties over multiple doses and lack of drug-drug interactions in repeated studies, that pharmacokinetics or tolerability would differ markedly in ALS subjects (no CYP metabolism; predominantly renal clearance). We thus chose a fixed dosing strategy with 600 mg/day and 900 mg/day arms to include two doses that were both likely to be tolerated and likely to reduce excitability. Importantly, we will determine whether the CSF concentration approaches the known EC50 of ~ 2  $\mu$ M from both our *in vitro* studies and heterologous expression of Kv7 channels (Wickenden et al., 2000). CSF levels were not measured in the epilepsy studies. With regard to study duration, the observed effects on hyperexcitability in the most relevant clinical studies (Caramia et al.,

2000; Stefan et al., 2001) were observed within the time frame (4 weeks of maintenance dose treatment) proposed in the study.

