## 3 OBJECTIVES

### 3.1 Study Objectives

The primary purpose of the proposed study is to determine whether ezogabine reduces neurophysiological excitability indices in ALS subjects as assessed by *axonal threshold NCS* and TMS. The study also will evaluate in ALS subjects dosing, safety and tolerability, and limited serum and CSF PK prior to a larger study designed to evaluate effect on a combined score of function and survival, should reduction in neurophysiological excitability indices be achieved.

Although motor neuron hyperexcitability has been repeatedly demonstrated in ALS subjects, two central questions relate to the use of such measures in clinical trials. First, it is not known if reducing excitability will influence the disease course. That is, the hyperexcitability may be a downstream property that results as a consequence of the neurodegenerative disease process, and blocking it might not affect clinical progression. While *in vitro* evidence from our work and that of other groups (Fritz et al., 2013) suggests that reducing activity may improve motor neuron survival *in vitro*, accurate mouse models exist only for SOD1 familial ALS (2% of total ALS cases) and thus the question can only be properly addressed in clinical studies of human subjects. Second, should a reduction in motor neuron excitability be capable of influencing the disease progression, it is not known what magnitude of reduction – particularly in the neurophysiological markers described in this proposal – would be clinically significant. Still, given the well-established differences between healthy control and ALS patients in both the TMS and *axonal hyperexcitability assessments*, a reasonable assumption is that reduction of excitability to the levels of controls may constitute a clinically relevant difference, and this study is sufficiently powered to detect that.

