### 13.3 Primary Analysis

We will test the effect of ezogabine on SICI using the mITT sample of ALS subjects in a shared-baseline mixed model with fixed effects for visit (6 levels: Screening, Baseline, and Weeks 4, 6, 8, and 12), treatment group (3 levels: placebo and 600 and 900 mg/day ezogabine) x post-baseline visit (4 levels) and random site-specific intercepts and random participant-specific intercepts and slopes with unstructured covariance. The use of a shared-baseline reflects the homogeneity of the trial cohort prior to randomization and the combination with participant-specific random effects induces an adjustment for any chance baseline differences similar to ANCOVA (Liu et al, 2009). We will use linear contrasts to test for dose-dependent differences in change from baseline to the average SICI over the stable dose period from weeks 6 through 8. A significant reduction of SICI (i.e., higher MEP amplitude) of either dose relative to placebo would be accepted as evidence of benefit from ezogabine treatment.

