### **13.8 Power Calculations**

Caramia et al. (2000) report mean (SD) paired pulse SICI at 3 ms among 16 ALS patients of 125.7 (25.7) percent of MEP control size. Stefan et al. (2001) report paired pulse SICI at 3 ms among 13 ALS patients of 96.9 (35.9) percent of MEP control size. Assuming a mean (SD) equal to 100 (30) percent of MEP and using a two-sided alpha of 0.027 based on Dunnett's correction for comparing two treatments to placebo, 40 patients in each group and up to 25% loss to follow-up would give 80% power to detect a 25% difference between placebo and each active treatment based on a simple two-sample t-test. This accommodates the loss of power due to early stopping for futility and is conservative relative to our proposed shared-baseline mixed model analysis. For reference, Caramia et al. (2000) report an effect of three-week exposure to gabapentin equal to an 80% reduction of the paired pulse amplitude in untreated patients, and Stefan et al. (2001) report an effect of 5 or more day exposure to riluzole equal to a 35% reduction of the conditioned stimulus amplitude.

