## 3.3 Measurement Definitions

### 3.3.1 TMS Measures

Transcranial magnetic stimulation (TMS) is a neurophysiologic test for assessing upper motor neuron function. A magnetic coil is positioned on the head above the motor cortex at a location that causes excitation of the abductor pollicis brevis (APB) muscle in a participant's dominant hand. High-frequency sampling of motor evoked potentials (MEP) in the APB is used to record neurophysiologic response to specific magnetic field strengths and sequences. The MEP traces are used to calculate a range of derived measures. MEPs that were below the limit of detect and recorded as zero mV were replaced by 0.005 mV.

- Resting motor threshold (RMT): RMT is the magnetic field strength, measured as a percentage of the maximum stimulator output, that produces at least a 0.05 mV response in at least 5 of 10 consecutive trials.
- MEP amplitude: MEP amplitude is defined as the response when a stimulus equal to 120% of RMT is administered. MEP amplitude is calculated as the geometric mean of replicate estimates.
- Short-interval intracortical inhibition (SICI): Paired-pulse SICI is defined as the ratio of the response after a conditioning pulse equal to 80% of RMT is administered 3 ms prior to the signaling pulse divided by MEP amplitude. SICI is calculated as the geometric mean of replicate estimates.
- Intracortical facilitation (ICF): Paired-pulse ICF is defined as the ratio of the response after a conditioning pulse equal to 80% of RMT is administered 15 ms prior to the signaling pulse divided by MEP amplitude. ICF is calculated as the geometric mean of replicate estimates.
- Cortical silent period (CSP): CSP is the suppression of voluntary muscle contraction elicited by stimulation equal to 120% of RMT. CSP duration is measured from the time of the muscle activity suppression to return of muscle activity.
- Input/Output curve parameters: MEPs elicited by stimuli ranging in strength from 60% of RMT to 150% of RMT follow a sigmoidal curve with upper and lower thresholds and a smooth, symmetric transition between the thresholds. A four-parameter logistic function fit to the input/output curve after log-transformation of output potentials yields estimates of maximum amplitude, minimum amplitude, midpoint of activation, and slope at the midpoint of activation.

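### Does the MEP amplitude gloss in Protocol 13.3 leave the direction of the primary success criterion in doubt?

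*Protocol*

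**What the plan says.** Protocol 13.3 closes its account of the primary model with the success rule: "A significant reduction of SICI (i.e., higher MEP amplitude) of either dose relative to placebo would be accepted as evidence of benefit".

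Two places fix the scale of SICI.
- **Protocol 13.8** expresses SICI as a percentage of the control MEP. One cited study of ALS patients is said to "report mean (SD) paired pulse SICI at 3 ms among 16 ALS patients of 125.7 (25.7) percent of MEP control size". The effect of riluzole in another is given as "equal to a 35% reduction of the conditioned stimulus amplitude".
- **SAP 3.3.1** gives the definition: "Paired-pulse SICI is defined as the ratio of the response after a conditioning pulse equal to 80% of RMT is administered 3 ms prior", continuing "3 ms prior to the signaling pulse divided by MEP amplitude". The denominator is defined just above it: "MEP amplitude is defined as the response when a stimulus equal to 120% of RMT is administered".

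The aim is to lower excitability. Protocol 2.2 says that "the primary goal of this study is to determine whether ezogabine treatment safely reduces neurophysiological indices of motor neuron hyperexcitability in ALS subjects", and Protocol 3.1 opens with "The primary purpose of the proposed study is to determine whether ezogabine reduces neurophysiological excitability indices in ALS subjects".

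SAP 3.8.1 states the success rule again. A significant mean fall in SICI on either dose, relative to placebo, is taken to show that the drug lowers cortical hyperexcitability. The sentence does not mention MEP amplitude. SAP section 1 gives the SAP precedence over the protocol on questions of analysis.

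**The concern.** The abbreviation i.e. claims that the two phrases mean the same thing, and on the documents' own definitions they do not. Taken at face value, the sentence can be read as counting a larger conditioned response as a benefit. That is the opposite of what a drug meant to calm motor neurons should produce.

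The sign matters more than usual here. The primary test is two-tailed, so significance alone does not separate a good result from a bad one. The protocol's outcome definition (3.2.1) speaks only of a change in SICI, and 13.6 speaks only of a significant benefit. Section 13.3 is therefore where the protocol says which direction of SICI counts. If that sentence governed, a significant rise in SICI could be claimed as a success, and it could open the gate to the key secondary outcome.

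**Working it through.** **The plan's own figure first.** The inputs, from Protocol 13.8 and SAP 3.4, are a difference of 25 on a mean of 100, SD 30, two-sided alpha 0.027, and 40 per arm less 25% loss. That leaves 40 × 0.75 = 30 evaluable per arm. The noncentrality is 25 / (30 × √(2/30)) = 25 / 7.746 = 3.23, and the two-sample t-test has power 82.8%. With 28 per arm power is 79.8% and with 29 it is 81.4%, so 29 / 0.75 = 38.7, rounded up to 39, would be enough. The stated 80% with 40 per arm is therefore met. The two-sided Dunnett critical value for two comparisons with a common control is 2.212, a per-comparison alpha of 0.02696, which rounds to the stated 0.027. None of these inputs refers to the direction of the effect.

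**The gloss against the definition.** Take SICI = conditioned response / unconditioned response (SAP 3.3.1), starting at 100/100. The changes below are assumed and show sign only.

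| Conditioned | Unconditioned | SICI | ln(SICI) |
|---|---|---|---|
| 100 | 100 | 1.00 | 0 |
| 125 | 100 | 1.25 | +0.223 |
| 75 | 100 | 0.75 | −0.288 |
| 100 | 125 | 0.80 | −0.223 |
| 125 | 125 | 1.00 | 0 |
| 150 | 125 | 1.20 | +0.182 |
| 60 | 80 | 0.75 | −0.288 |

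- *MEP amplitude means the conditioned response.* A higher value raises SICI (1.25) and a lower one reduces it (0.75). The gloss is reversed.
- *SICI means the amount of inhibition.* Less inhibition does go with a higher conditioned MEP, so the gloss describes the phrase correctly. The fault is then that loss of inhibition is counted as benefit, against Protocol 2.2, Protocol 3.1 and SAP 3.8.1. This reading also sits badly with Protocol 13.8, where SICI is an amplitude percentage.
- *MEP amplitude means the unconditioned response, as SAP 3.3.1 defines it.* A higher denominator lowers the ratio only if the numerator does not rise in step: 0.80, 1.00 and 1.20 are all possible at 125. The ratio can also fall to 0.75 with a lower denominator (60/80). The gloss is not reversed here, but it is not equivalent to a lower SICI.

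So the gloss is faulty on every reading, though not in the same way on each.

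**Whether anything depends on it.** The analysis needs a scale, a sign and a rule for conflicts.
1. *Scale.* SAP 3.3.1 makes SICI a ratio, and SAP 3.8.1 analyses its logarithm. This removes the reading of SICI as an amount of inhibition.
2. *Sign.* SAP 3.8.1 says that a mean reduction shows lower cortical hyperexcitability. On the log scale that is a negative contrast, or a proportional change below 1 after back-transformation.
3. *Conflict.* SAP section 1 gives the SAP precedence on analysis.

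The protocol on its own also points the same way. Protocol 2.1 says that gabapentin in one cited ALS study and riluzole in another reduced cortical hyperexcitability. Protocol 13.8 reports the effects in those two studies as reductions of 80% in the paired-pulse amplitude and 35% in the conditioned amplitude. Lower excitability therefore goes with a lower paired-pulse response.

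**With and without the gloss.** The model, contrast, alpha, sample size and gate are identical, and power stays at 82.8% with 30 evaluable per arm. If the true effect were a 25-point fall, the chance of a significant result in the opposite direction would be about 4 × 10⁻⁸.

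**The case for a change.** The best case for an amendment is that a precedence clause settles which document governs but does not make the other one right. The protocol is read on its own by sites, ethics boards and later readers. Its one explicit statement of which direction of SICI counts as success carries a gloss that misdescribes it. The SAP fixes the direction only when 3.3.1 and 3.8.1 are read together, and it does not mention the discrepancy. Deleting a few words would cost almost nothing.

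Much of this stands. The wording is wrong, it is ordinary running text in the current protocol version, and nobody should defend it. What does not follow is that the direction of the primary test is open. The gloss is an aside; the criterion is a reduction of SICI, and that agrees with the SAP. Someone with only the protocol still has the stated aim in 2.2 and 3.1, the amplitude scale in 13.8, and the cited drug effects, all pointing to a lower ratio as the favourable result. The person who runs and reports the analysis works from the SAP, where the question does not arise.

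**Conclusion.** The inconsistency is real and editorial. The gloss conflicts with the scale used in Protocol 13.8 and with the SAP definition of SICI, but it feeds into no calculation and no decision rule. Its effect on the estimate, p-value, gate, sample size and power is nil. An analyst following the plan as written will call a lower SICI ratio on ezogabine than on placebo the favourable direction, and will be right to do so.

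This rests on two things in the documents: the SAP's precedence on analysis, and its definition of SICI as conditioned response over MEP amplitude read together with the direction in 3.8.1. The percentages in the table are assumed and carry no weight beyond their sign. If the protocol were reopened for another reason, the parenthesis could simply be dropped, but the point does not justify an amendment.

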### 13.4 Secondary Analyses

We will use the same shared-baseline mixed model analysis to test other continuous secondary efficacy outcomes (additional TMS parameters, NCS parameters, ALSFRS-R, and SVC). MEP threshold, the key secondary outcome, will be tested prior to and separate from all other secondary efficacy outcomes. We will compare trajectories in TMS and NCS parameters between ALS and matched healthy control subjects in an augmented model with the addition of fixed effects for patient group (2 levels: ALS and healthy controls) and patient group x visit interactions (9 levels: 6 visits for ALS patients and 3 for matched healthy controls) and separate patient-level variance-covariance and residual variance estimates by patient group. Comparisons between matched healthy controls and ALS patients will be estimated using linear contrasts.

Safety and tolerability will be compared across treatments by log-rank test of time to first SAE, time to death, and time to dose discontinuation and by negative binomial regression of overall SAE and AE rates. The proportion of participants experiencing each MedDRA-classified AE will be compared across treatment groups by Fisher's exact test. Treatment-dependent differences in suicidality will be estimated from C-SSRS total scores analyzed using the same shared-baseline mixed model used for the primary analysis.

Serum PK estimates will be obtained for  $C_{max}$  and time to peak concentration.

Associations between firing rate of iPSC-derived motor neurons and baseline *in vivo* neurophysiological excitability indices will be compared within and between ALS and healthy control subjects by linear regression with *in vivo* paired pulse SICI as the dependent variable and

*in vitro*-firing rate, disease status and their interaction as predictors. A change-point model will be explored with a break at each participant's *in vitro*-estimated EC50 for blocking motor neuron spontaneous action potential firing by ezogabine. Spontaneous firing rate of the *in vitro*-derived motor neurons and *in vitro*-estimated EC50 for blocking motor neuron spontaneous action potential firing by ezogabine will be considered as moderators of treatment efficacy in tests of neurophysiological and clinical response by augmenting the shared-baseline mixed models with fixed effects for iPSC parameters, the two-way interaction with visit, and the three-way interaction with treatment group and post-baseline visit.

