### **Study Objectives and Endpoints**

The primary efficacy outcome is change in paired pulse short-interval intracortical inhibition (SICI) assessed by transcranial magnetic stimulation (TMS) after treatment with 600 mg/day or 900 mg/day of ezogabine vs. matched oral placebo. Change in motor evoked potential (MEP) threshold is the key secondary efficacy outcome. Additional upper motor neuron secondary outcomes include MEP amplitude, MEP latency, cortical silent period, and paired pulse facilitation, assessed by TMS. Lower motor neuron excitability outcomes include change in electrotonus, recovery cycle and strength duration time constant as determined by threshold tracking axonal nerve conduction studies (NCS) and CMAP amplitude. The effect of retigabine on strength will be assessed using hand held dynamometry, and muscle symptoms will also be assessed utilizing a subject muscle symptom diary, in which the subjects will record the frequency, location and severity of their muscle cramps and fasciculations over the course of study treatment. Additional secondary outcomes include dosing, tolerability and safety of ezogabine in ALS patients. Serum and optional cerebrospinal fluid (CSF) sampling will be collected (at Week 6) for limited pharmacokinetic (PK) analysis and banking.

Exploratory outcomes include *in vitro* analysis of subject iPSC-derived motor neurons and *in vitro* response of motor neuron firing to ezogabine treatment. We will also recruit approximately 72 healthy control subjects to perform quality control analysis for the neurophysiology testing (approximately 60 healthy controls) and to correlate differences between ALS subjects and healthy controls as assessed using *in vitro* measurements of hyperexcitability compared to using the *in vivo* neurophysiological ones (approximately 12 healthy controls). Healthy control subjects will undergo neurophysiological testing but not be treated with drug or placebo. Approximately sixty (60) healthy control subjects will be evaluated prior to ALS subjects, to assess test-retest and inter-investigator variability for the neurophysiology measurements. Approximately twelve (12) healthy control subjects will be recruited in parallel with the ALS subjects, to allow an age and site-matched comparison between ALS and healthy control subjects. These 12 healthy control subjects will also undergo blood sampling for iPSC generation.

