### **Number of Planned Subjects**

Approximately 192 subjects will be enrolled in this study. Approximately sixty (60) healthy controls will be enrolled for assessment of short-term reliability of TMS and NCS measurements (approximately five (5) from each site) prior to recruiting ALS subjects. Approximately twelve (12) additional healthy controls will be age and site-matched and enrolled in parallel with the ALS subjects. An initial sample of 45 ALS subjects will be recruited and randomized prior to an interim futility analysis. If the trial of one of the two active treatment groups is not stopped early for futility or safety, then approximately 120 ALS subjects will be recruited in total.

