#### **Matched Healthy Control Group (12):**

Approximately 1 Healthy Control/Site  
3 Neurophysiology Visits Over 12 weeks

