### **5.3 Inclusion and Exclusion Criteria for Healthy Controls (Unmatched and Matched)**

#### **5.3.1 Inclusion Criteria**

Healthy control volunteers meeting all of the following criteria will be allowed to enroll in the study:

1. Male or female, aged 18 to 80.
2. Capable of providing informed consent and following trial procedures.
3. Geographically accessible to the site.
4. Use of medications known to affect the neurophysiology measures in the study must be scheduled, not as needed (pro re nata, PRN). A subject must have been on a fixed dose for 30 days prior to the Screening Visit, and there must be no reason to believe that a subsequent change would be necessary during the course of the study. These medications include: benzodiazepines, muscle relaxants, tricyclic antidepressants, selective serotonin reuptake inhibitors, non-selective serotonin reuptake inhibitors, hypnotics (including anti-histamines) and anti-cholinergics.
5. Age (+/- 10 years and site-matched to a ALS participant within 6 months of their Baseline visit).**[Matched controls only]**
6. TMS shows sufficient MEP amplitude and/or NCS studies show sufficient CMAP amplitude (amplitudes defined in MOP).

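### The Protocol 13.4 model comparing ALS participants with matched controls has no age term, so the age matching is not carried into the analysis

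*Protocol*

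**What the plan says.** The Protocol Summary (Study Objectives and Endpoints) gives the purpose of the second control group: "to allow an age and site-matched comparison between ALS and healthy control subjects". Protocol 5.3.1, criterion 5, sets the rule: "Age (+/- 10 years and site-matched to a ALS participant within 6 months of their Baseline visit". On numbers, the Summary says "Approximately twelve (12) additional healthy controls will be age and site-matched and enrolled in parallel with the ALS subjects", and the workflow gives "Approximately 1 Healthy Control/Site". About 120 ALS participants are planned (Protocol 5.1).

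The analysis is in Protocol 13.4: "We will compare trajectories in TMS and NCS parameters between ALS and matched healthy control subjects in an augmented model". It takes the shared-baseline mixed model of 13.3, whose random part is "random site-specific intercepts and random participant-specific intercepts and slopes with unstructured covariance", and extends it "with the addition of fixed effects for patient group (2 levels: ALS and healthy controls) and patient group x visit interactions", plus separate variance estimates for the two groups. Then: "Comparisons between matched healthy controls and ALS patients will be estimated using linear contrasts". No age covariate is listed, there is no pair effect, and the ALS side is not restricted to the participants to whom controls were matched (the index participants below).

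A second ALS-control analysis in 13.4, the iPSC regression, has SICI as the outcome and firing rate, disease status and their interaction as predictors. It has no age term either.

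The SAP adds nothing here. Its Introduction limits it to the ALS participants of the randomised trial, and it contains no ALS-control model. Its Overview (2.1) does say that controls are enrolled to look at disease differences both at baseline and over time.

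**The concern.** By matching on age, the protocol treats age as something the ALS-control comparison must control. Matching one control per site does this for the 12 index participants. The model, however, sets those 12 controls against the whole ALS cohort, and no term accounts for any age difference between the two.

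This matters for levels as well as trajectories. SAP 2.1 names baseline differences as an aim, and Protocol 3.1 uses the level seen in controls as the benchmark for a possibly relevant reduction in excitability. If a TMS or NCS measure varies with age, a gap in mean age shifts that benchmark.

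**Working it through.** The documents give no sample size, power or effect for the ALS-control comparison, so there is no planned figure to reproduce. Protocol 13.8 and SAP 3.4 cover the randomised comparison only.

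**1. Matching factors against model terms.** Site is matched, and is in the model as a random intercept. Age is matched, and is not in the model. The pairs are formed at recruitment and not used.

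**2. Coverage.** 120 − 12 = 108 ALS participants have no matched control.

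**3. Chance gap in mean age.** Assumptions: age SD *s* of 8, 11 or 14 years; index participants picked at random; control-minus-index age difference uniform within ±10 years, so its variance is 10²/3 = 33.3 and the mean of 12 has variance 33.3/12 = 2.78.

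- 12 controls against all 120 ALS: SD = √[*s*²(1/12 − 1/120) + 2.78]
- 12 controls against their 12 index participants: SD = √2.78
- 12 unmatched controls from the same age distribution, against all 120: SD = √[*s*²(1/12 + 1/120)]

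| Assumed *s* | Planned comparison | 12 pairs only | Unmatched |
|---|---|---|---|
| 8 | 2.75 | 1.67 | 2.42 |
| 11 | 3.44 | 1.67 | 3.33 |
| 14 | 4.18 | 1.67 | 4.24 |

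Against the whole cohort without an age term, chance age balance is about what unmatched controls of the same age distribution would give.

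**4. Effect on a level contrast.** With *s* = 11 and an assumed age-outcome correlation *r* of 0.2 to 0.4, the shift is *r* × gap / 11 in outcome SDs.

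- 3.44 years (one SD of the chance gap): 0.06 to 0.13
- 5 years: 0.09 to 0.18
- 10 years: 0.18 to 0.36

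For scale, the SE of a simple baseline contrast is √(1/12 + 1/120) = 0.30 SD.

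**5. Level against change.** Suppose age adds *b* per year to the level and *c* per year per month to the slope. A gap *g* then biases the level contrast by *bg* and the change to month *t* by *cgt*; *b* cancels from the change.

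A simulation checked this: 12 sites, 10 ALS and 1 control per site, 150 runs per row, no treatment effect, age SD 11. Assumed SDs were 0.3 for site, 0.5 for participant intercept, 0.1 per month for slope and 0.4 for residual, with *b* = 0.02. Change is to Week 6 (*t* = 1.5). The adjusted model adds age and age × time. Entries are the mean ALS-minus-control estimate; the true value is 0.

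| Control ages relative to index | *c* | Level, no age | Level, adjusted | Change, no age | Change, adjusted |
|---|---|---|---|---|---|
| Symmetric | 0 | −0.002 | −0.015 | 0.038 | 0.039 |
| Symmetric | 0.005 | −0.009 | −0.011 | 0.022 | 0.021 |
| 5 years younger on average | 0 | 0.131 | 0.020 | −0.004 | −0.002 |
| 5 years younger on average | 0.005 | 0.091 | −0.003 | 0.047 | 0.012 |
| 10 years younger | 0 | 0.161 | −0.037 | 0.009 | 0.014 |
| 10 years younger | 0.005 | 0.196 | −0.003 | 0.097 | 0.018 |

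The formulas give a level bias of 0.02 × 5 = 0.10 and 0.02 × 10 = 0.20. With *c* = 0.005 they give a change bias of 0.005 × 5 × 1.5 = 0.04 and 0.005 × 10 × 1.5 = 0.08. Simulation SEs are about 0.013 to 0.018 and a few entries lie about 2.5 SEs from expectation, so read the table for its pattern. Level bias follows the gap and adjustment removes it. Change is biased only when age acts on the slope.

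**The case against.** Several points on the other side are sound.

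- **The quoted analysis concerns trajectories.** A reader might infer that any age trend enters the disease contrast. It does not: a stable age effect cancels from within-person change. For the same reason, an age main effect alone would do nothing for the change contrasts.
- **The matching is not lost.** A reader might infer that it is. But site stays in the model, and the 10-year limit bounds each control's distance from the index participant. That guards against a control group of quite different age, which the unmatched column in the working does not represent.
- **Ignoring the pairs is not an error.** Adjusting for the matching factors is a legitimate alternative. A pairs-only analysis drops about 108 ALS participants and raises the simple SE from 0.30 to √(2/12) = 0.41 SD, before any gain from pairing. After baseline it also mixes disease with drug, because 1:1:1 allocation puts about 8 of 12 index participants on ezogabine.
- **A chance gap is not a systematic bias.** Its expectation is zero under representative index participants and symmetric differences, and nothing in the documents points to a one-sided gap. The shift from a typical chance gap (0.06 to 0.13 SD) is well inside the SE. A 10-year gap would need every control at the same end of the limit, or a chance event of about 10/3.44 = 2.9 SDs.
- **The stakes are limited.** This is a secondary, unrandomised comparison with no stated power and no place in the multiplicity plan (Protocol 13.6).

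What survives is the omission. Age is a declared matching factor, level differences are an aim, and neither the model nor the SAP accounts for age.

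**Conclusion.** The concern holds in a limited form. Age matching is applied at recruitment and then not carried into the Protocol 13.4 analysis, so ALS-control differences in level can reflect age. Differences in change can do so only if age also affects the rate of change.

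The size cannot be fixed from the documents, which give neither an age SD nor an age effect. Under the assumptions above, the likely shift is small next to the contrast's own SE. It becomes comparable with that SE only for a one-sided gap near the 10-year limit together with the stronger assumed age correlations. The documents do not support saying that the comparison is biased or that the matching served no purpose. They support saying that a known, measured factor is left unadjusted where adjusting costs almost nothing. The randomised primary and key secondary comparisons are not touched.

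**What to change.** In Protocol 13.4, add centred age at screening and age × visit (or age × time) as fixed effects to the augmented model, and keep the random site intercept. The main effect serves the level contrasts and the interaction serves the change contrasts. Add age to the ALS-control iPSC regression.

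Optionally, record each control's index participant and run a sensitivity analysis in the 12 pairs at baseline only, before treatment can enter the difference.

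Demographics are already collected at screening in both groups, so the cost is a sentence or two of text and, if the pair analysis is wanted, one further model run. In the simulation, adjustment cost no precision: the SD of the level estimate was 0.19 to 0.23 without age and 0.18 to 0.22 with it. The remaining assumption is that one linear age effect serves both groups, since 12 controls are too few to estimate their own reliably.
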